APPENDIX 4:

ANALYSIS CODE FOR THE STUDY

* Compare Baseline Characteristics; * continuous variables; proc means data=smarter data mean std; var IS age SBP0 DBP0 GLU0 NHDL0 waist0 BMI0 risk0 risk lifetime 0; by group; run; * categorical variables; proc freq data=smarter data; tables male pd education pd labor pd income pd married pd insure smk daily 0 PA 1t3000 0; by group; run; * Evaluation of Research Outcomes; data fu4 data; set smarter data; if risk4^=.; run; proc means data=fu4 data n mean std; var risk0 risk4 risk lifetime 0 risk lifetime 4 SBP0 SBP4 DBP0 DBP4 GLU0 GLU4 NHDL0 NHDL4; by group; run; proc freq data=fu4 data; tables obesity 0 obesity 4 smk daily 0 smk daily 4 PA lt3000 0 PA lt3000 4 LTPA0 LTPA4; by group; run; proc means data=fu4 data n mean clm; var risk4_change risk_lifetime4_change SBP4_change DBP4_change GLU4_change NHDL4 change; by group; run;

* model for continuous variables (eg.10-y ASCVD risk);

proc glimmix data=fu4_data;

class village_id group(ref='2') male education_high_above Last_year_income_lt_10k
occupation_farmer marriage_yes insure_yes vc_risk_grp vc_sbp_grp vc_age_grp
doctor_college_above;
model risk4_change=group risk0 IS_age male education_high_above
Last_year_income_lt_10k occupation_farmer marriage_yes insure_yes vc_risk_grp
vc_sbp_grp vc_age_grp doctor_college_above
/solution dist=normal link=identity ddfm=bw cl ;
random int/subject=village_id type=un;
run;

* model for categorical variables (eg.smk daily);

proc glimmix data=fu4_data;

class village_id group(ref='2') male education_high_above Last_year_income_lt_10k
occupation_farmer marriage_yes insure_yes smk_daily_0 vc_risk_grp vc_sbp_grp
vc_age_grp doctor_college_above;
model smk_daily_4(event="1") =group smk_daily_0 IS_age male education_high_above
Last_year_income_lt_10k occupation_farmer marriage_yes insure_yes vc_risk_grp
vc_sbp_grp vc_age_grp doctor_college_above/solution dist=binary link=logit ddfm=bw cl;
random int/solution subject=village_id type=un;
ods output ParameterEstimates=Coefficients_smk;
run;

data coefficients_smk; set coefficients_smk; if effect~='Intercept' then do; PA_OR=exp(Estimate); PA_OR_L=exp(Estimate-1.96*stderr); PA_OR_U=exp(Estimate+1.96*stderr); PA_OR_95CI=compress(put(PA_OR,4.2))||"("||compress(put(PA_OR_L,4.2))||","||compress(p ut(PA_OR_U,4.2))||")"; end; run; * Subgroup Analysis;

* eg.sex: male/female;

data male; set fu4_data; if male=1; run; data female; set fu4_data; if male=0; run;

proc means data=male n mean clm; var risk4_change; by group; run;

proc glimmix data=male;

class village_id group(ref='2') education_high_above occupation_farmer

Last_year_income_lt_10k marriage_yes insure_yes vc_risk_grp vc_sbp_grp vc_age_grp doctor_college_above;

model risk4_change=group risk0 IS_age education_high_above occupation_farmer Last_year_income_lt_10k marriage_yes insure_yes vc_risk_grp vc_sbp_grp vc_age_grp doctor_college_above/solution dist=normal link=identity ddfm=bw cl;

random int/subject=village_id type=un;

run;

proc means data=female n mean clm; var risk4_change; by group; run;

proc glimmix data=female;

class village id group(ref='2') education high above occupation farmer

Last_year_income_lt_10k marriage_yes insure_yes vc_risk_grp vc_sbp_grp vc_age_grp doctor college above;

model risk4_change=group risk0 IS_age education_high_above occupation_farmer Last_year_income_lt_10k marriage_yes insure_yes vc_risk_grp vc_sbp_grp vc_age_grp doctor_college_above/solution dist=normal link=identity ddfm=bw cl ; random int/subject=village_id type=un; run; * test for interaction;

proc glimmix data=fu4_data;

class village_id group(ref='2') male education_high_above occupation_farmer

Last_year_income_lt_10k marriage_yes insure_yes vc_risk_grp vc_sbp_grp vc_age_grp

doctor_college_above;

model risk4_change=group risk0 IS_age male male*group education_high_above

occupation_farmer Last_year_income_lt_10k marriage_yes insure_yes vc_risk_grp

vc_sbp_grp vc_age_grp doctor_college_above

/solution dist=normal link=identity ddfm=bw cl;

random int/subject=village_id type=un;

run;

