3. SAMPLE SIZE

The sample size for the proposed trial was calculated based on the primary outcome. At the time of the study design, we calculated a minimum sample size of 4200 participants in 120 villages (60 villages in each comparison group, and 35 participants in each village), which would provide a statistical power of 90% with a two-sided significance level of 0.05 to detect an 1.0% absolute difference in the 12-month change of 10-year risk of ASCVD between the intervention and control groups. The calculation assumed a standard deviation (SD) of 6.0% for both the intervention and control groups at baseline, an intra-cluster correlation coefficient (ICC) of 0.04, and allowed a loss of follow-up of 10%.

To compensate for the risk of entire-village withdrawing, the study screened more villages at enrolment. At last, a total of 4533 participants from 127 villages were included. With an actual ICC of 0.06, the statistical power finally achieved was 88%.

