6. STATISTICAL ANALYSES

6.1 Baseline Characteristics

Descriptive statistics will be used to summarize the baseline characteristics of the whole cohort of the study participants and by study groups: continuous variables will be presented as mean and standard deviation, or medians, interquartile range, minimum and maximum, and categorical variables as frequencies and percentages.

T-test/Wilcoxon rank sum test will be used to compare continuous variables between the intervention and control group. The Chi-square test/Fisher exact test will be used to compare the categorical variables between the two groups.

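### The within-arm 95% intervals for continuous changes ignore village clustering; full-arm primary intervals are about 41–43% too narrow, while between-arm results are unaffected

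*Combined protocol and SAP*

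**What the plan says.** Protocol 3.2.2 and SAP 3.3 make the village the unit of randomisation. SAP 6.3 and 6.4 include the village as a random effect in the between-group models, and the Appendix 4 GLIMMIX code does so too, including the interaction test.

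The within-arm changes are handled differently. Under the outcome-evaluation heading of Appendix 4, the step is "proc means data=fu4 data n mean clm; var risk4_change risk_lifetime4_change SBP4_change DBP4_change" and so on for six continuous change variables, by group. The worked subgroup example, sex, repeats the pattern: "proc means data=male n mean clm; var risk4_change; by group; run". Neither step has a village term. In Tables S6(a) and S6(b) the change columns stand beside net differences; the Table S6(a) footnote describes the net differences as adjusted for village clustering and does not say that the change columns are not.

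For baseline, SAP 6.1 states: "T-test/Wilcoxon rank sum test will be used to compare continuous variables between the intervention and control group". It names chi-square or Fisher tests for categorical variables. Neither allows for villages.

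The SAP sample-size section gives two ICCs: a design value, in "an intra-cluster correlation coefficient (ICC) of 0.04, and allowed a loss of follow-up of 10"%, and a realised one, in "With an actual ICC of 0.06, the statistical power finally achieved was 88"%.

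**The concern.** The CLM option of PROC MEANS computes the mean plus or minus t × SD/√n, which treats some 2,200 villagers per arm as independent. They are not: the SAP's own ICC is above zero, and each village contributes about 35 people. The resulting interval understates the uncertainty of the arm's mean change.

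The primary outcome is itself a mean change from baseline, so these are prominent figures. One table row now carries two kinds of 95% interval under the same label, one ignoring the design and one respecting it. A reader who judges the arms by their own intervals sees more precision than the trial has. The baseline tests in SAP 6.1 make the same omission.

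**Working it through.** **1. Reproduce the stated power, to confirm the ICC and cluster size.** Inputs from the SAP sample-size section: difference 1.0%, SD 6.0%, two-sided alpha 0.05, 4533 participants in 127 villages (35.7 per village), ICC 0.06. Design effect (DEFF) = 1 + (m − 1) × ICC; effective n per arm = n / DEFF.

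- No loss: DEFF = 1 + 34.7 × 0.06 = 3.08; effective n = 2266.5 / 3.08 = 736; power 89.2%.
- 10% loss applied to n and m (m = 32.1): DEFF 2.87; effective n = 2040 / 2.87 = 711; power 88.2%.
- 10% loss applied to n only: power 85.8%.

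The stated 88% is reproduced by the second variant and lies close to the first.

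**2. Shortfall of a full-arm interval.** The unclustered width is the correct width divided by √DEFF, so the shortfall is 1 − 1/√DEFF.

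| ICC | m | DEFF | √DEFF | Shortfall | Actual coverage |
|---|---|---|---|---|---|
| 0.06 | 31.5 | 2.83 | 1.68 | 41% | 76% |
| 0.06 | 35 | 3.04 | 1.74 | 43% | 74% |
| 0.06 | 35.7 | 3.08 | 1.76 | 43% | 74% |
| 0.04 | 31.5 | 2.22 | 1.49 | 33% | 81% |
| 0.04 | 35 | 2.36 | 1.54 | 35% | 80% |
| 0.04 | 35.7 | 2.39 | 1.55 | 35% | 80% |

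(m = 31.5 is 35 less 10% loss.)

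**3. Applied to the primary outcome in Table S6(a), ICC 0.06, m = 35.**

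- Intervention: half-width 0.25 × 1.744 = 0.44, so -6.3 (-6.7 to -5.9).
- Control: half-width 0.30 × 1.744 = 0.52, so -4.2 (-4.7 to -3.7).

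**4. A check that assumes no ICC.** Take each within-arm SE as interval width / 3.92, combine the arms as √(SE₁² + SE₂²), and compare with the SE of the net difference from the mixed model (width / 3.92). For 10-year risk: SEs 0.128 and 0.153, combined 0.199; model SE 1.38 / 3.92 = 0.352.

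| Outcome | Combined within-arm SE | Model SE | Shortfall |
|---|---|---|---|
| 10-year risk | 0.199 | 0.352 | 43% |
| Lifetime risk | 0.397 | 0.834 | 52% |
| SBP | 0.523 | 0.857 | 39% |
| DBP | 0.307 | 0.548 | 44% |

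With a multiplier of 1.98 in place of 1.96 for the model SE, the SBP figure is 38%; the others move by less than one point. Rounding of the printed limits allows 33–54% for 10-year risk. Fasting glucose and non-HDL-C are rounded too coarsely to use. The model SE is the larger one even though the model adjusts for baseline level and covariates, which would ordinarily reduce it.

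**5. Subgroups, same method on Table S6(b).** The shortfall runs from about 3% (high school and above: 0.451 against 0.467) to 45% (below high school: 0.199 against 0.362). Nine of the twelve rows are below 40%. Fewer members per village mean a smaller design effect.

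**6. Baseline tests.** A z of 1.96 becomes 1.96/√DEFF. With m = 35, an unclustered P of 0.05 becomes 0.09 at ICC 0.01 (DEFF 1.34), 0.13 at 0.02, 0.20 at 0.04 and 0.26 at 0.06. No ICC is given for any baseline variable, so this range is an assumption.

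**The case against.** The strongest reply is that no planned inference rests on these intervals. SAP 6.3 and 6.4 plan only between-group comparisons, and those use a village random intercept throughout. The corrected primary intervals, (-6.7 to -5.9) and (-4.7 to -3.7), still do not overlap, so a reader comparing the arms reaches the same conclusion. This stands, and it limits the point to reporting.

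Three wider readings are tempting, and the documents do not support them.

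- *That every change interval is 40–50% too narrow.* That range fits the full-arm primary outcome at ICC 0.06. It is 33–35% at ICC 0.04, and a 50% shortfall at 35 per village would need an ICC near 0.09 (DEFF 4.0), which the documents do not give. Most subgroup rows fall below 40%.
- *That all the change columns are affected.* The code shown covers continuous variables only. It does not show how the intervals for obesity, daily smoking or the activity measures were made.
- *That baseline P values are far too small.* The Appendix 4 baseline code requests only means, SDs and frequencies, and no baseline P value appears in the documents reviewed. Age, SBP and 10-year risk were minimisation factors, so allocation pushes them towards balance and a simple design-effect error rate does not apply to them.

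It is also fair to say that a crude within-arm change and a covariate-adjusted net difference are different quantities, so the SE comparison in step 4 supports the result only approximately.

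**Conclusion.** The point holds for the continuous outcomes. The code for the within-arm intervals omits the village, and at the SAP's actual ICC the full-arm primary intervals are about 41–43% too narrow, with coverage near 74–76% instead of 95%. The reported results point the same way, at about 38–52% for 10-year risk, lifetime risk, SBP and DBP. Subgroup shortfalls range from about 3% to 45%.

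Three assumptions matter. The SAP does not name the variable behind the ICC of 0.06; it is read here as the primary outcome because it stands in that outcome's sample-size section. Villages are treated as equal in size. Table S6 excludes participants with MACEs, and it is taken to have been produced by the Appendix 4 code or its equivalent; only the sex subgroup is written out there.

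Net differences, their P values and the interaction tests are sound on this point. The baseline tests are a secondary flaw in the SAP text, of unknown size and with no sign in the code that they were run. Overall this is a moderate reporting correction that leaves the trial's conclusion as it is.

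**What to change.** 1. Take the within-arm changes and 95% intervals for continuous outcomes from a model with a village random intercept (LSMEANS by group), or use village-robust standard errors, in every table and every subgroup.
2. State how the intervals for the binary changes were computed, and use a cluster-aware method for them.
3. In SAP 6.1, delete the t, Wilcoxon, chi-square and Fisher tests and report descriptive statistics or standardised differences. This also brings the SAP into line with the Appendix 4 baseline code.

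The cost is a few lines of code, wider within-arm intervals and one edited SAP paragraph. No new data are needed, and the between-arm estimates stay the same.

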3.6 Outcome Evaluation

The information of study outcomes (for participants in both intervention and control groups) was collected at baseline and each follow-up visits at 3th month, 6th month, 9th month, and 12th month. All the data collection was conducted using standardized equipment and following uniform operational protocols. These data were collected in three ways: (1) standardized electronic questionnaire interview; (2) physical examination; (3) fingertip blood sample collection.

The primary outcome, 10-year risk of ASCVD, was calculated by the China-PAR prediction model based on age, sex, geographic region (northern/southern China), urbanity, waist circumference, systolic blood pressure (SBP), use of antihypertensive

medication, presence of diabetes, total cholesterol (TC), high-density lipoprotein cholesterol (HDL-C), smoking status, and family history of ASCVD.

Regarding assessment of the metabolic risk factors, to be more specific, blood pressure was measured twice on the right upper arm using a standard sphygmomanometer (Omron HEM-7121, Omron Corporation, Japan) after 5 minutes of rest in the sitting position. Blood glucose and blood lipid were tested by the rapid blood glucose analyser (BeneCheck BK6-20 M Multi-Monitoring System, Suzhou Pu Chun Tang Biotechnology, China) and the fast photochemical lipid analyser (CardioChek PA Analyzer; Polymer Technology Systems, USA), respectively. Body mass index (BMI) was calculated as body weight in kilograms divided by the squared value of height in meters, with obesity was defined as a BMI≥28.0 kg/m².

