6.4 Analysis of Secondary Outcomes

The secondary outcomes included mean changes in the levels of lifetime risk of ASCVD based on the China-PAR model, SBP, DBP, FBG, and non-HDL-C, as well as changes in the proportions of obesity, daily smoking, and insufficient physical activity, from baseline to the 12 months. The assessment of secondary outcomes of continuous variables will be analysed using linear mixed effects models, same as the analysis method of primary outcome, and the categorical variables will be analysed using the generalised linear mixed effects models. Villages will be adjusted in the

models as a random effect. The net differences between the two groups were assessed by the models, with multivariable adjustment by baseline covariates including age, sex, education, occupation, annual household income, marital status, and social medical insurance.

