Control	(992/2212)	(1295/2197)	(1395/2207)	(1480/2203)	(1556/2200)	P<0.001*
(Mean change	e) Interventior	1: 35.6% (33.5	% to 37.8%),	Control: 25.9%	6 (23.8% to 27.9	%)

Table S5. Exploratory Outcome: Medication adherence

* Medication adherence was defined as taking the full dose of prescribed medications ≥6 days per week among all participants with hypertension, diabetes, or dyslipidaemia. The net group difference was adjusted for clustering effects by villages (as random effect), four minimisation factors, age, sex, education, occupation, annual household income, marriage status, social medical insurance, and baseline level of the outcome.

Fig S4. Exploratory Outcome: MACEs

* The HR and 95%CI of MACEs were estimated by Cox frailty model with adjustment of clustering effects by villages (as random effect), four minimisation factors, age, sex, education, occupation, annual household income, marriage status, and social medical insurance.

	Intervention (n=2246)				Control (n=2	2188)	Net Group Difference	Darahar
	Baseline	12-month	Change (95%CI)	Baseline	12-month	Change (95%CI)	(95%CI)	P value
Primary outcome								
10-year risk of ASCVD, %	18.0 (7.1)	11.7 (5.8)	-6.3 (-6.5 to -6.0)	17.7 (6.8)	13.5 (6.9)	-4.2 (-4.5 to -3.9)	-1.88 (-2.57 to -1.19)	< 0.001
Secondary outcomes								
Lifetime risk of ASCVD, % *	49.9 (15.4)	34.0 (12.7)	-15.9 (-16.4 to -15.3)	49.4 (15.8)	38.4 (14.8)	-11.0 (-11.5 to -10.4)	-4.59 (-6.23 to -2.96)	< 0.001
Systolic blood pressure, mmHg	157.7 (16.2)	134.4 (12.1)	-23.2 (-23.9 to -22.5)	157.0 (16.1)	141.9 (16.1)	-15.0 (-15.8 to -14.3)	-7.70 (-9.38 to -6.02)	< 0.001
Diastolic blood pressure, mmHg	93.4 (11.0)	82.5 (8.0)	-10.9 (-11.3 to -10.4)	92.6 (10.7)	85.8 (9.8)	-6.8 (-7.2 to -6.4)	-3.63 (-4.70 to -2.55)	< 0.001
Fasting blood glucose, mmol/L	7.2 (2.7)	6.3 (1.6)	-0.9 (-1.0 to -0.8)	7.1 (2.5)	6.6 (1.8)	-0.5 (-0.6 to -0.4)	-0.29 (-0.51 to -0.07)	0.009
Non-HDL-C, mmol/L	3.4 (1.2)	3.0 (1.1)	-0.4 (-0.4 to -0.3)	3.4 (1.3)	3.1 (1.1)	-0.3 (-0.4 to -0.3)	-0.06 (-0.19 to 0.08)	0.43
Obesity	869 (38.7%)	784 (34.9%)	-3.8% (-5.0% to -2.6%)	842 (38.5%)	792 (36.2%)	-2.3% (-3.5% to -1.1%)	0.83 (0.65 to 1.05)	0.13
Daily smoking	515 (22.9%)	449 (20.0%)	-2.9% (-4.0% to -1.9%)	473 (21.6%)	462 (21.1%)	-0.5% (-1.5% to 0.4%)	0.61 (0.43 to 0.85)	0.004
Insufficient physical activity	315 (14.0%)	247 (11.0%)	-3.0% (-4.6% to -1.5%)	309 (14.1%)	337 (15.4%)	1.3% (-0.3% to 2.8%)	0.63 (0.42 to 0.94)	0.03
(<3000 MET-min/wk)								

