Insufficient leisure-time activity (<150/75 min/wk)	1541 (68.6%)	1040 (46.3%)	-22.3% (-24.7% to -19.9%)	1420 (64.9%)	1372 (62.7%)	-2.2% (-4.5% to 0.1%)	0.38 (0.24 to 0.59)	< 0.001

* Data were mean (SD), n (%), mean (95%CI) or OR (95%CI) unless otherwise stated.

All net group difference was adjusted for clustering effects by villages (as random effect), four minimisation factors, age, sex, education, occupation, annual household income, marriage status, social medical insurance, and baseline level of the outcome.

	Interv	ention (n=2246)	Co	ntrol (n=2188)	Net Group Difference	D l	D :
Subgroup	Number	Changes (95%CI)	Number	Changes (95%CI)	(95%CI)	P value	P-inter
Age, year							0.73
<60	1352	-7.0 (-7.3 to -6.6)	1301	-5.2 (-5.6 to -4.9)	-1.86 (-2.57 to -1.16)	< 0.001	
≥60	894	-5.2 (-5.6 to -4.8)	887	-2.7 (-3.1 to -2.3)	-1.82 (-2.63 to -1.01)	< 0.001	
Sex							0.03
Male	1130	-7.2 (-7.6 to -6.7)	1062	-4.6 (-5.0 to -4.2)	-2.20 (-3.05 to -1.36)	< 0.001	
Female	1116	-5.4 (-5.7 to -5.1)	1126	-3.8 (-4.1 to -3.5)	-1.55 (-2.20 to -0.90)	< 0.001	
Education							0.74
Below high school	1755	-6.0 (-6.3 to -5.7)	1749	-4.1 (-4.4 to -3.9)	-1.83 (-2.54 to -1.12)	< 0.001	
High school and above	491	-7.3 (-7.9 to -6.7)	439	-4.4 (-5.0 to -3.7)	-2.11 (-3.03 to -1.20)	< 0.001	
Occupation							0.03
Farmer	1535	-6.1 (-6.4 to -5.8)	1465	-4.4 (-4.7 to -4.0)	-1.63 (-2.41 to -0.85)	< 0.001	
Non-farmer	711	-6.6 (-7.1 to -6.1)	723	-3.8 (-4.3 to -3.4)	-2.60 (-3.37 to -1.83)	< 0.001	
Annual household income, yuan							0.02
<10 000	358	-5.1 (-5.8 to -4.5)	347	-2.4 (-3.1 to -1.8)	-2.76 (-3.90 to -1.63)	< 0.001	
≥10 000	1888	-6.5 (-6.8 to -6.2)	1841	-4.5 (-4.8 to -4.2)	-1.72 (-2.40 to -1.03)	< 0.001	
10-year risk of ASCVD, %							< 0.001
<16	1128	-3.5 (-3.7 to -3.3)	1128	-2.3 (-2.6 to -2.0)	-1.14 (-1.76 to -0.52)	< 0.001	
≥16	1118	-9.0 (-9.5 to -8.6)	1060	-6.2 (-6.6 to -5.8)	-2.57 (-3.42 to -1.72)	< 0.001	

 Table S6 (b). Subgroup results of the primary outcome (sensitivity analysis: excluding participants with MACEs)

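### The obesity model most likely adjusts only for yes/no baseline obesity; adding the baseline BMI already in the dataset would recover about a fifth in information on that one secondary outcome

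*Combined protocol and SAP*

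**What the plan says.** SAP Section 6.4 states that "categorical variables will be analysed using the generalised linear mixed effects models", with village as a random effect and seven demographic and socioeconomic covariates. It names no baseline value of the outcome.

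Appendix 4 prints one such model, labelled "model for categorical variables (eg.smk daily". Its right-hand side includes "group smk_daily_0 IS_age male education_high_above", so baseline enters as a 0/1 class variable. The obesity model is not printed. Obesity appears in the code only as two indicators, in "tables obesity 0 obesity 4 smk daily 0 smk daily 4".

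The footnote to Table S6(a) in Appendix 3 says that adjustment covered "social medical insurance, and baseline level of the outcome", without giving the form of that covariate.

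SAP Section 3.6 says that "obesity was defined as a BMI≥28.0 kg/m²". Continuous baseline BMI is in the analysis dataset, in "var IS age SBP0 DBP0 GLU0 NHDL0 waist0 BMI0 risk0 risk lifetime 0", but it is used there only for baseline means and enters no printed model.

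**The concern.** A 0/1 baseline covariate gives a person at BMI 28.1 and one at BMI 36 the same predicted chance of being obese at month 12. Nearly all changes of status occur close to the cut: in simulation, about 93% came from people within 1.5 units of 28. The indicator cannot represent this, and BMI0 can.

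What is at stake is precision on the one adiposity outcome in the results table. Its odds ratio there is "0.83 (0.65 to 1.05", P = 0.13. No new data would be needed to do better.

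**Working it through.** **1. Reproduce the reported row (Table S6(a), Obesity).** SE(log OR) = ln(1.05/0.65)/(2 × 1.96) = 0.122. z = ln(0.83)/0.122 = −1.52. Two-sided P = 0.128, which matches the printed 0.13.

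**2. How many people changed status.** For a paired change in proportion, share changing = n × SE² + d². Both arms have a half-width of 1.2 points, so SE = 0.012/1.96 = 0.00612.
- Intervention: n = 2246, d = (784 − 869)/2246 = −0.0378. Share = 0.0842 + 0.0014 = 0.0856, or about 192 people: 139 lost and 54 gained obesity.
- Control: n = 2188, d = (792 − 842)/2188 = −0.0229. Share = 0.0820 + 0.0005 = 0.0825, or about 181 people: 115 lost and 65 gained.

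**3. Which baseline covariate does the row look like?** Stratifying these counts on baseline obesity gives odds ratios of (730/139)/(727/115) = 0.83 to 0.84 among the obese and (54/1323)/(65/1281) = 0.80 among the others. Pooled by inverse variance, the OR is 0.82 with SE 0.11 before any clustering. The reported 0.83 with SE 0.122 fits this plus modest clustering. The unadjusted OR is (784/1462)/(792/1396) = 0.945. In the simulation of step 5, adjustment for BMI0 gives about 0.77. This supports the reading that obesity_0 was used but does not prove it.

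**4. Individual-level loss, no clustering.** With both arms pooled, 254 of 1711 obese people lost and 119 of 2723 others gained obesity, so the rates are 0.148 and 0.044. Mean residual variance given obesity_0 = (1711 × 0.148 × 0.852 + 2723 × 0.044 × 0.956)/4434 ≈ 0.074. If baseline and 12-month BMI are bivariate normal, the share changing status fixes their correlation at about 0.965, and mean residual variance given BMI0 is about 0.056. The ratio is about 1.33 (1.31 to 1.38 over rounding of the printed intervals).

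**5. With villages.** The documents give no BMI SD, BMI-change SD or village SD, so these are assumptions: 127 villages of 35, baseline BMI SD 3.5, individual change SD 0.95, village SD of change 0.25. These settings give about 8.5% changing status, an OR of about 0.83 and SE(log OR) 0.124, close to the trial's figures.

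| Quantity | obesity_0 | BMI0 |
|---|---|---|
| SE, standardised risk difference | 0.0093 | 0.0084 |
| Mean z | −1.54 | −1.71 |
| SE(log OR) | 0.124 | 0.150 |
| Conditional OR | 0.83 | 0.77 |

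- Risk-difference variance ratio: (0.0093/0.0084)² = 1.23.
- Squared-z ratio: (1.71/1.54)² = 1.23.
- Log-OR variance: (0.150/0.124)² = 1.46, so it rises.
- Range: with village SD from 0.5 down to 0, BMI0 lowers the risk-difference variance by 11% to 24%, equivalent to about 12% to 31% more participants. Random-intercept logistic fits, including skewed BMI and heavy-tailed changes, gave squared-z ratios of 1.19 to 1.36.
- BMI0 beside obesity_0 performed the same as BMI0 alone. Rejection under the null was 4% to 7%.

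**6. What it means for the row.** Expected z = 1.52 × √1.2 = 1.67 (P about 0.10), or 1.52 × √1.3 = 1.74 (P about 0.08). Power at z = 1.54 is Φ(1.54 − 1.96) = 34%; at 1.71 it is Φ(1.71 − 1.96) = 40%. For a true effect of 2.6 points, power would go from about 79% to 88%. The observed crude difference is smaller: 3.8 − 2.3 = 1.5 points.

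**The case against.** The strongest objection is the scale. The trial reports a conditional odds ratio, and a reader might infer that the variance of that estimate is a fifth larger than it needs to be. It is not. The odds ratio is non-collapsible: adding BMI0 moves it further from 1 and widens its interval on the log scale. The simulations put the rise in log-OR variance at 26% to 69%. The gain appears only in z (power) or in a standardised risk difference, which the trial does not report. This objection stands and fixes how the point must be put.

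The obesity model is not in the documents. The template is an example for smoking, and the footnote does not exclude BMI as the baseline level. This also stands; obesity_0 is the likely reading, supported by step 3.

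Adjusting a binary outcome for its binary baseline is conventional and valid. The results already exist, so a new covariate prompted by P = 0.13 could look results-driven. That bears on how the analysis is labelled, not on whether BMI0 is the more informative covariate.

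**Conclusion.** The point holds as a modest loss of precision on one secondary outcome. If obesity was modelled with obesity_0 alone, about 20% in information is given up, range roughly 10% to 35%, on the squared-z or standardised risk-difference scale. The size rests on assumed BMI and village SDs, calibrated to the printed change intervals.

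Three stronger inferences are not supported:
- The non-significant obesity row is not explained by the covariate. The expected P remains about 0.08 to 0.10, and neither bias nor a type I error problem was found.
- Table S6(a) is a sensitivity analysis that excludes participants with MACEs. The main-analysis obesity result is not in these documents, so nothing follows about it directly.
- The loss does not extend in any material way to the other binary outcomes. Using baseline MET-min/wk for physical inactivity gains only 2% to 4%, and smoking was not quantified.

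**What to change.** In SAP Section 6.4, state that the obesity model includes continuous BMI0, in a linear or spline form fixed in advance, beside obesity_0, and add the term to the code. Keep the odds ratio. Alongside it, give the model-standardised difference in proportions with an interval that allows for villages, since that is where the gain can be seen.

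Because results are already tabulated, report this as a sensitivity analysis or as a deviation described and justified in the final report, as SAP Section 1 requires. Leave the inactivity model as it is.

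Cost: no new data, one sentence in the SAP, one covariate, and a little more code, because the printed procedure does not output the standardised difference. A functional form must be chosen, and the BMI0-adjusted odds ratio will not be comparable with the one adjusted for obesity_0 only, which the report should say.

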3.3 Randomisation and Blinding

The group assignment was conducted by a central randomisation system based on minimisation algorithm. The villages served as the units of randomisation. The assignment was stratified by county, and was conducted after all participants within each county had been recruited and baseline survey data had been collected. Factors that were balanced between the comparison groups include participants' age, systolic blood pressure, and 10-year risk of ASCVD, as well as the education attainment of the village doctor. Random numbers were generated by an independent statistician using a computer. A random element of 0.9 were introduced to enhance unpredictability in the allocation process.

Due to the nature of the cluster design and the intervention programme, the village doctors and the study participants were aware of their group allocation. However, the allocation will be concealed from the study statisticians.

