6.3 Analysis of Primary Outcomes

The primary outcome of the trial is the mean changes in 10-year risk of ASCVD based on the China-PAR model from baseline to the 12 months. Linear mixed effects model will be used to compare the primary outcome between the intervention group and the control group. The dependent variable is the change in 10-year risk of ASCVD of the participants from baseline to the 12-month, and the independent variable is the study group. Villages will be adjusted in the model as a random effect. The net difference between the two groups was assessed by the model, with multivariable adjustment by baseline covariates including age, sex, education, occupation, annual household income, marital status, and social medical insurance.

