6.5 Subgroup Analyses

Potential interactions will be explored for the primary outcome by subgroups of age, sex, education, occupation, annual household income, and tertile of baseline 10-year risk of ASCVD, with a statistical significance level of 0.05 (two-sided).

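### The interaction test shown has only a random village intercept, so if a subgroup factor's effect varies between villages its P value may be too small

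*Combined protocol and SAP*

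**What the plan says.** SAP 3.3 states that "The villages served as the units of randomisation". SAP 6.5 plans the interaction tests: "Potential interactions will be explored for the primary outcome by subgroups of age, sex, education, occupation, annual household income, and tertile" of baseline risk, "with a statistical significance level of 0.05 (two-sided"). It names no model or random-effect structure for them. SAP 6.3, for the primary outcome, says only that "Villages will be adjusted in the model as a random effect".

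The structure is visible only in the Appendix 4 code. The interaction model there, with sex as a labelled example, has the fixed part "model risk4_change=group risk0 IS_age male male*group education_high_above" and further covariates. Its one random statement is "random int/subject=village_id type=un", and its options are "solution dist=normal link=identity ddfm=bw cl". The documents give no random slope, no village-robust variance and no estimate of how much a factor's effect varies between villages.

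Appendix 3, Table S6(b), prints interaction P values of 0.73 (age), 0.03 (sex), 0.74 (education), 0.03 (occupation), 0.02 (income) and below 0.001 (baseline risk). These come from the sensitivity set that excludes participants with MACEs.

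**The concern.** Group varies only between villages and sex varies within them, so group by sex is a cross-level interaction. A random intercept lets villages differ in mean change but holds the male-female gap constant across the villages of an arm. Each village has its own doctor delivering a tailored programme, so the gap could well differ from one village to another. If it does, the between-arm contrast of gaps rests partly on 127 village-level gaps, whereas the model treats it as resting on about 4,400 people. Between-within degrees of freedom follow the same logic, because they give the interaction person-level degrees of freedom.

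The code is also not uniform. The separate models for men and for women let each sex have its own village effects, while the interaction model imposes one shared effect.

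Three of the four interactions below 0.05 lie between 0.02 and 0.03. They leave little room for an understated standard error, and a reader could take them as evidence on who benefits.

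**Working it through.** **Inputs.** Table S6(b): net difference in men -2.20 (-3.05 to -1.36), in women -1.55 (-2.20 to -0.90). Numbers of men are 1130 and 1062, and of women 1116 and 1126 (intervention, control). Table S6(a): overall -1.88 (-2.57 to -1.19). Villages: 127, assumed to split 64 and 63. Not in the documents: the village SD of the gap, written τ below, which is varied over a range.

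**1. The printed sex P of 0.03.** The strata differ by 2.20 - 1.55 = 0.65. P = 0.03 corresponds to z = 2.170, so the implied SE is 0.65/2.170 = 0.300. An error made up only of within-village variation would be σ × √(1/1130 + 1/1062 + 1/1116 + 1/1126), which needs σ of about 5.0. That is plausible, so the printed P is what an intercept-only model would give.

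**2. Adding village variation in the gap.** SE² = 0.300² + τ² × (1/64 + 1/63), with 1/64 + 1/63 = 0.0315.

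| τ (points) | SE | sex P | simulated type I error, intercept-only test |
|---|---|---|---|
| 0 | 0.300 | 0.030 | 4.9% |
| 0.5 | 0.312 | 0.038 | 5.9% |
| 0.8 | 0.331 | 0.050 | 7.1% |
| 1.0 | 0.348 | 0.062 | 9.4% |
| 1.5 | 0.401 | 0.105 | 15.1% |
| 2.0 | 0.464 | 0.162 | 20.2% |

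The simulation used 127 villages of 35 people and 2,000 runs per row, with assumed residual SD 5 and village SD 1.8. A test based on village-level differences stayed between 4.8% and 6.2% for τ from 0.5 to 2.0. P reaches 0.05 when SE = 0.65/1.96 = 0.332, that is, at τ of about 0.80. The same formula puts the crossing near τ = 1.2 for occupation (difference 0.97) and 1.6 for income (difference 1.04). Those two are rougher, because the strata are unequal in size.

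**3. What the printed intervals suggest about τ for sex.** Dividing CI widths by 3.92 gives SEs of 0.431 (men), 0.332 (women) and 0.352 (overall). Treat the overall effect as a weighted mean of the two strata, with weight w = 2192/4434 = 0.494 for men. The covariance between strata is then

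(0.352² - w² × 0.431² - (1-w)² × 0.332²) / (2w(1-w)) = 0.101,

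a correlation of 0.70. The SE of the difference is √(0.431² + 0.332² - 2 × 0.101) = 0.307, which does not assume τ = 0. It gives P = 0.034, or 0.023 to 0.047 allowing for rounding of the intervals. Against 0.300 it corresponds to τ of about √((0.307² - 0.300²)/0.0315), or roughly 0.4, with zero inside the rounding range.

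**4. The same route for the other factors.** Occupation gives P = 0.013 (printed 0.03), income 0.034 (printed 0.02) and baseline risk below 0.001.

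**5. Outer limit.** If the two strata shared no village effect at all, P would be 0.23 for sex, 0.083 for occupation, 0.124 for income and 0.008 for baseline risk. Baseline risk stays significant even there. Age and education are non-significant either way.

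**The case against.** A reader might infer that the printed subgroup P values are too small, or that the sex interaction is not really significant. The documents do not support either reading. Understatement requires τ above zero, and no slope variance is reported. The SE recovered from the intervals does not assume a constant gap, yet it leaves sex, occupation and income all below 0.05, and for occupation it gives a smaller P than the one printed. The rows of the table above that exceed 0.05 rest on chosen values of τ, not estimated ones.

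The implied-SE step is also fragile. The strata come from separate models with their own covariate effects, so their difference need not equal the interaction estimate. For age (difference 0.04, P 0.73) the step gives an SE of 0.116 against 0.303 recovered from the intervals. For education (0.28, P 0.74) it gives 0.844, larger than the 0.591 expected with independent strata. The sex figures are therefore indicative only.

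Finally, SAP 6.5 presents these analyses as exploratory, the printed P values come from a sensitivity set, and only the sex code is shown.

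All of this stands, and it limits the size of the concern. It does not remove the structural point: nothing in the plan makes the test hold its stated 0.05 level if a factor's effect varies by village.

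**Conclusion.** The point holds as a conditional one. The interaction model shown omits village-to-village variation in the subgroup effect, and if such variation exists the P values may be too small. The inflation is slight at a gap SD of 0.5 points (about 6% type I error), moderate at 0.8 to 1.0 (7% to 9%) and serious only at larger values. For sex, the printed intervals point to the low end, with P of about 0.034, so loss of significance is possible but not shown.

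Only the exploratory sex, occupation and income P values have a conclusion at stake. The primary comparison is unaffected, since group is a village-level term there and the village intercept carries the relevant error. That the other factors were tested with the same structure is inferred from the sex code being labelled an example. The figures rest on a 64/63 village split, the assumed simulation variances and, for sex, the approximate implied SE.

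**What to change.** State the interaction model in SAP 6.5 and change the Appendix 4 code in one of two ways.

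- Keep the intercept-only model, but use village-clustered empirical standard errors with a small-sample correction.
- Or add a village random slope for each subgroup factor. The factor needs care in the RANDOM statement: the code declares male as a CLASS variable, so adding it under type=un would request an over-parameterised 3 × 3 matrix (intercept plus two sex levels). Enter it as a numeric 0/1 indicator if type=un is kept. Replace ddfm=bw for the interaction with village-level degrees of freedom, about 127 - 2 = 125. By itself that change is small: at an SE of 0.300 the sex P moves from 0.030 to 0.032.

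Report the slope variance, and the interaction P from the new fit beside the intercept-only P, so that a reader can see whether the choice matters. The sponsor holds the data and can settle this directly.

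The cost is a line or two of code per interaction model. The interaction P values may become slightly larger, and a slope variance may be estimated at zero; in that case the intercept-only result is supported and little is lost.
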